6.4.3 Planned Analyses

6.4.3.1 Primary Analyses

Percentage of good quality embryo formation between control and experimental arm will be analyzed using McNemar's test.

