5.3.1 Number of Participants

As this study will be randomizing oocytes, and therefore the number of participants will depend on the average number of oocytes retrieved per patient. Following power calculation, 408 oocytes are needed for randomization in order to detect a significant difference in our primary outcome. If 6 oocytes are obtained from each patient enrolled in the study, then 68 patient/sperm source dyads will be enrolled.

Based on our 2020 data, there was a total of 1,680 mature oocytes from 137 retrievals that produced 6 or more mature oocytes for ICSI insemination, from 121 different patients. The average number of mature oocytes within ICSI cycles with 6 or more mature oocytes obtained was 12 mature oocytes. Based on this data, we anticipate 138 patient cycles are needed for this study and this could include up to 138 patient/sperm source dyads.

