6.1.2 Device administration and schedule

Patient/sperm source dyads enrolled in the study and meeting inclusion criteria will have their sperm sample prepared prior to, or near the time of, oocyte retrieval. Semen parameters will be recorded prior to separation. Semen will be split and separated via ZyMot and density gradient.

Density gradient will be performed as follows:

- Density gradient centrifugation will be performed using a one-layer preparation of 90% Isolate (Irvine Scientific) in 15 mL conical tubes. Semen will be layered over 1 mL of gradient and then centrifuged for 15 min at 300xg. The supernatant will be removed and discarded. The sperm pellet will be washed by mixing with Multipurpose Handling Medium Complete (Irvine Scientific) and centrifuging the sample for 5 min at 400xg. After the wash, the supernatant is removed and discarded and the pellet is re-suspended in culture medium (Continuous Single Culture-NX Complete, Irvine Scientific), assessed for sperm parameters, and held at room temperature until insemination.

ZyMot separation using the Multi (850 uL) microfluidic separation device will be performed as follows:

- 850 uL of untreated semen will be directly deposited into the inlet port of the ZyMot™ Multi device, followed by placement of 750 uL culture medium (Continuous Single Culture- NX complete, Irvine Scientific) in the outlet port and throughout the upper collection chamber. The device will then be incubated in a humidified 37C CO2 incubator for 30 minutes. During incubation, the healthiest and most motile sperm will swim through the microporous filter and into the upper collection chamber, where they will be recovered via the outlet port. 500 uL of the sperm sample will be removed and placed in a separate tube for analysis and insemination.
- After sperm processing, sperm parameters will be evaluated and recorded for each preparation, including sperm concentration, percent motility, and grade of forward progression. The density gradient preparation results will be recorded as Sample 1 in the electronic medical record (eMR) system gamete sheet. The ZyMot preparation results will be recorded as Sample 2 in the eMR system gamete sheet.

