- Following oocyte retrieval, oocytes will be denuded of their cumulus cells per standard protocol. If at least 6 mature oocytes (determined by visualization of a polar body) are present, half the oocytes will be ICSI inseminated with sperm prepared via ZyMot device and half will be ICSI inseminated with sperm prepared with density gradient. Patients whose patient identification number (PID) is even will have the group of oocytes inseminated with sperm separated via ZyMot device recorded first in the eMR gamete sheet (beginning with oocyte #1.) Patients with an odd PID will have the oocytes inseminated with sperm separated via density gradient recorded first in the eMR gamete sheet (beginning with oocyte #1.) In the event of an odd number of oocytes, the patients with even PIDs will have the extra oocyte inseminated with sperm separated via Zymot device and patients with odd PIDs will have the extra oocyte inseminated with sperm separated via density gradient. Inseminated oocytes will be grouped into separate wells of a LifeGlobal 4 well GPS dish (Cooper Surgical) by the sperm separation method — one well will contain all oocytes inseminated with sperm selected by ZyMot device and a separate well will contain all oocytes inseminated with sperm selected by density gradient centrifugation.

Control Group of Oocytes:

Half of the eggs will be inseminated via ICSI using sperm selected by conventional gradient centrifugation.

Treatment Group of Oocytes:

- Half of the eggs will be inseminated via ICSI using sperm selected using ZyMot.
- Fertilization assessment will be performed between 16 and 18 hours after insemination and normal fertilization will be considered visualization of exactly two pronuclei. Normally fertilized oocytes (embryos) will then be cultured in Continuous Single Culture Medium — NX Complete (Irvine Scientific) in separate, numbered droplets in LifeGlobal microdrop GPS dishes (Cooper Surgical.) The numbers of the droplets will correlate to oocyte/embryo number in the eMR gamete sheet and, thereby, also correlate to the type of sperm used for the insemination. Development of the embryos will be assessed on culture days 5 and 6 and embryo stage and grade will be recorded for each embryo.

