6.1.3 Method of Assignment/Randomization

Patient/sperm source dyads meeting inclusion criteria and enrolled in the study will have their sperm sample prepared prior to or near the time of oocyte retrieval. Semen parameters will be recorded prior to separation. Semen will be split and separated via ZyMot and density gradient.

Following oocyte retrieval, oocytes will be denuded of their cumulus cells per standard protocol. If at least 6 mature oocytes (determined by visualization of a polar body) are present, half the oocytes will

be ICSI inseminated with sperm separated via ZyMot device and half will be ICSI inseminated with sperm prepared with density gradient. Patients whose patient identification number (PID) is even will have the group of oocytes inseminated with sperm separated via ZyMot device recorded first in the eMR gamete sheet (beginning with oocyte #1.) Patients with an odd PID will have the oocytes inseminated with sperm separated via density gradient recorded first in the eMR gamete sheet (beginning with oocyte #1.) In the event of an odd number of oocytes, the patients with even PIDs will have the extra oocyte inseminated with sperm separated via Zymot device and patients with odd PIDs will have the extra oocyte inseminated with sperm separated via density gradient.

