6.4 Statistical Method

6.4.1 Statistical Design

All data will be de-identified and then will be analyzed by a statistician. Descriptive statistics of the study sample will be calculated (mean \pm standard deviation or median [25th, 75th percentiles] for continuous variables; frequency and percent for categorical data. Paired analyses will be performed. A result will be considered statistically significant at the $p < 0.05$ level of significance. All analyses will be performed using SAS version 9.4 (SAS Institute Inc., Cary, NC).

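### The primary McNemar test needs oocyte pairs that the plan never defines, and no rule says how the extra oocyte in odd cohorts enters the table, so the plan does not determine the primary p-value

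*Combined protocol and SAP*

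**What the plan says.** The primary test is given in section 6.4.3.1: "Percentage of good quality embryo formation between control and experimental arm will be analyzed using McNemar's test". The only other general statement is in section 6.4.1: "Paired analyses will be performed". Neither says what a pair is.

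Sections 6.1.2 and 6.1.3 describe how the data arise. A patient's mature oocytes, six or more, are halved between the arms and recorded one arm after the other: "Patients whose patient identification number (PID) is even will have the group of oocytes inseminated with sperm separated via ZyMot device recorded first", and the reverse for odd numbers. Until the fertilization check the arms are held in bulk: "one well will contain all oocytes inseminated with sperm selected by ZyMot device", with a separate well for the gradient arm. Each arm of a cycle uses one preparation of one sample: "Semen will be split and separated via ZyMot and density gradient".

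Odd cohorts are foreseen: "In the event of an odd number of oocytes, the patients with even PIDs will have the extra oocyte inseminated" with ZyMot sperm, and patients with odd PIDs have it inseminated with gradient sperm. This is an allocation rule. Neither section 6.1.3 nor section 6.4 says what happens to that oocyte in the analysis.

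Section 6.4.3.2 adds a separate analysis of the same endpoint that accounts for same-patient correlation and cohort size. It names conditional logistic regression and generalized estimating equations (GEE) together. The interim comparison (sections 6.4.3.5 and 7.12) uses the same endpoint at p < 0.05 and names no test.

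**The concern.** McNemar's test works on a table of matched yes/no pairs. This trial produces, for each patient, a count of good embryos out of three or more oocytes in each arm. Reading the patient as the pair does not help, because a patient's result in an arm is a proportion, and no section turns it into a yes/no outcome. Somebody must therefore decide which ZyMot oocyte is compared with which gradient oocyte and, in odd cohorts, which oocyte of the larger arm is left out.

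Both decisions can change the p-value on identical data. Two statisticians who follow the plan faithfully could report different primary results, and nothing in the plan would say which is right. The gap carries over to the interim comparison if McNemar's test is used there. Leaving out randomised oocytes also discards data for no reason other than the choice of test.

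**Working it through.** **Inputs from the documents.** Section 6.4.2: rates of 48% and 55% (a 7-point difference), r = 0.5, two-sided 0.05, 408 oocytes, 68 dyads of 6. Section 5.3.1: "1,680 mature oocytes from 137 retrievals that produced 6 or more mature oocytes for ICSI insemination, from 121 different patients", so 1,680/137 = 12.3 per retrieval.

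**Assumptions.** Patient effect on the logit scale with SD 0.6 or 1.0; patient-by-arm preparation effect with SD 0 or 0.5; 34 patients as an alternative to 68, from 408/12. Section 5.3.1 also says "we anticipate 138 patient cycles are needed for this study", but at six or more oocytes each that is at least 138 x 6 = 828 oocytes, which does not fit 408. That conflict is a separate matter, and 138 cycles are not used here.

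**Plan's own figure.** n = 16pq(1-r)/d² = 16 x 0.515 x 0.485 x 0.5 / 0.07² = 1.9982/0.0049 = 407.8, rounded up to 408; 408/6 = 68. The figure reproduces. Whether n counts eggs or pairs is a separate question.

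**Why the statistic is not fixed.** McNemar's statistic is (b-c)²/(b+c), where b and c are the two kinds of discordant pair.
- Equal arms: b-c is the difference in successes, so it is fixed. b+c is not. For one patient with 4/6 against 3/6, pairing can give b = 1, c = 0 (sum 1) or b = 3, c = 2 (sum 5).
- Unequal arms: take 2/4 on ZyMot and 1/3 on gradient. Leaving out a ZyMot success gives b-c = 1-1 = 0; leaving out a failure gives 2-1 = 1. The numerator now changes too.

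**Two simulated data sets, even cohorts.** Both have 112 v 98 successes out of 204 per arm, so b-c = 14 and (b-c)² = 196. They were generated with an assumed latent within-patient correlation of 0.7. The ranges cover 1,000 random within-patient pairings.

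| Cohorts | b+c | Statistic | p |
|---|---|---|---|
| 68 x 3 per arm | 48 to 74 | 4.08 to 2.65 | 0.043 to 0.104 |
| 34 x 6 per arm | 38 to 60 | 5.16 to 3.27 | 0.023 to 0.071 |

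**How often it matters.** The measure is the chance that two independent outcome-blind choices fall on opposite sides of 0.05, i.e. the mean of 2q(1-q), where q is the share of choices with p < 0.05. It was computed over 1,500 trials of 400 choices each, at 48% v 55%.
- Even cohorts (68 x 6 or 34 x 12 oocytes): 2.2-2.6%.
- 34 patients averaging 12, odd counts allowed: 7.5-8.7%. About 17 cohorts are odd, so about 17/408 = 4% of oocytes are left out.
- The same 34 patients with the left-out oocyte fixed and only the pairing free: 2.4-2.9%. The missing rule for the extra oocyte is therefore the larger part.

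A separately coded repeat (600 trials of 300 choices) gave about 1.8% (68 x 3 per arm), 2.3-2.8% (34 x 6 per arm) and 8.1-8.3% (odd counts). When the median p lies near 0.05, the central 95% of choices runs from about 0.036 to 0.064 with even cohorts and 0.018 to 0.11 with odd counts.

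**Type I error** (both arms at 51.5%, 20,000-30,000 trials per setting).

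| Test | No preparation variation | Preparation SD 0.5 (assumed) |
|---|---|---|
| McNemar, random blind pairing | 4.8-5.2% | 6.3-8.9% |
| CMH stratified by patient | 4.9-5.0% | 8.4-9.4% |
| Patient-clustered GEE, corrected SE | 4.8-5.2% | up to 5.4% |

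**The case against.** The strongest reply is that the gap is small and partly covered. Two blind choices agree in about 91-98% of trials. Section 6.4.3.2 already plans a correlation-adjusted analysis of this endpoint, and the documented scenario of 68 dyads with exactly six oocytes has no odd cohorts, which puts it at the 2-3% end. All of this is true. But the adjusted analysis is an addition under secondary objectives and does not say which of its two named methods is fitted, so it cannot settle the primary p-value. The plan itself provides for odd cohorts.

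One could also pair by position in the gamete sheet. The plan does not say so. Nor does it describe tracking single oocytes within the shared well; numbered droplets come in only for normally fertilized oocytes. If numbers were settled after that check, positional pairing might not be blind to outcome.

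The assumed patient SDs imply a within-patient phi of only about 0.08-0.17, against the plan's r = 0.5. Raising the SD to about 2.7 to match r = 0.5 leaves disagreement similar, at 2.9% and 8.6%.

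Three stronger readings are tempting, and the documents do not support them:
- That there is no rule at all for the extra oocyte. Sections 6.1.2 and 6.1.3 allocate it by PID parity; only its place in the analysis is missing.
- That McNemar's test is biased here. With blind within-patient pairing it holds 5% under ordinary patient clustering. The excess error appears only with an assumed preparation SD that the documents do not give.
- That a large share of trials is at risk because some pairing somewhere crosses 0.05. That share grows with the number of pairings tried, so it is not a measure of two analysts disagreeing.

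**Conclusion.** The point holds as under-specification of the primary analysis and should be fixed before any analysis. The stated test does not fit the data structure. Pairs are undefined, and in every odd cohort one randomised oocyte must be discarded by an unstated choice. Two statisticians following the plan would reach opposite conclusions at 0.05 in about 2-3% of trials with even cohorts and about 7-9% with 34 patients and odd counts. These figures assume 48% v 55%, 408 oocytes, a patient logit SD of 0.6-1.0 and choices made blind to outcome.

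A conditional point goes with it. All oocytes of an arm in a cycle share one sperm preparation, so if the preparation effect varies between samples McNemar's error rises above 5%: about 6-9% at an assumed logit SD of 0.5. The documents give no SD, so this supports choosing a clustered analysis but does not show that the planned test is invalid.

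**What to change.** Replace McNemar's test in section 6.4.3.1 with one pre-specified analysis of all randomised oocytes that needs no pairs.

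- Preferred: a patient-clustered analysis. For example, GEE for a good or fair day 5-6 blastocyst (yes/no) with arm as factor and independence working correlation, a small-sample-corrected robust SE with a t reference, and a risk difference with 95% CI. Cluster on patient, not cycle, since the 2020 data show 137 retrievals from 121 patients. This weights oocytes equally; if patients should be weighted equally, state that estimand instead. It also covers preparation variation.
- Minimum: a Cochran-Mantel-Haenszel test stratified by patient. It leaves out no oocyte but does not cover preparation variation.

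Name the same test for the interim comparison in sections 6.4.3.5 and 7.12, and replace the mixed model wording in section 6.4.3.2 with one defined model.

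No new data are needed. Without preparation variation the clustered test loses 0.2-1.6 points of power against McNemar (for example 31.5% to 30.8% at 68 x 3 per arm, 34.2% to 32.6% at 34 x 6), and the 95% half-width grows by 0.1-0.3 points. The stratified test costs no power (31-35% against 30-34%). The low power of all these tests at 408 oocytes is not caused by this change and belongs with the separate sample-size question in section 6.4.2.

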6.4.2 Sample Size Considerations

For a two-tailed McNemar's test with alpha level 0.05, the following relation yields an approximate power of 80% to detect a difference d between proportions p_1 and p_2 : $n = \frac{16pq(1-r)}{d^2}$ where n is the size of the sample (i.e. number of eggs), $p = (p_1 + p_2)/2$, $q = 1 - p$, $d = |p_2 - p_1|$, and r is the phi

correlation coefficient¹. We will assume a conservative estimate for the correlation $r=0.5$. Assuming a 48% good quality blastocyst development rate and a 7% improvement in good quality blastocyst development with ZyMoT, we would need a total of 408 oocytes randomized to either density gradient or ZyMoT separation, which would equate to 68 patient/sperm source dyads each with ≥ 6 eggs retrieved.

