6.4.3.2 Secondary Objectives Analyses

Sperm parameters following ZyMot and density gradient sperm separation, as well as Euploid rates in the event that PGT-A was performed following ICSI comparing sperm separation with ZyMot to density gradient, will be assessed using the paired t-test, Wilcoxon signed rank test, or a generalized linear mixed model (GLMM). A random subject-specific intercept and an unstructured correlation structure will be used to account for within-subject correlation between rates between the two groups. Data will be reported as least squares means with corresponding 95% confidence intervals.

Pregnancy outcomes will be assessed using McNemar's test. The difference in good quality blastocyst development rate and pregnancy outcomes between the ZyMot and density gradient separation groups will also be analyzed separately using a conditional logistic regression model with generalized estimating equations to account for both correlation between observations from the same patient and the size of the cohort of eggs from each patient.

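### The primary McNemar test has no pairing rule and no clustering adjustment; under within-dyad pairing its p-value is too small if outcomes vary between sperm preparations

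*Combined protocol and SAP*

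**What the plan says.** - **Primary test (6.4.3.1).** "Percentage of good quality embryo formation between control and experimental arm will be analyzed using McNemar's test". Section 6.4.1 adds only that analyses are paired and that the threshold is 0.05. No section gives a pairing rule or a clustering adjustment for this test.
- **Sample size (6.4.2).** The trial is sized for a "two-tailed McNemar's test with alpha level 0.05", with n counted in eggs. The inputs are stated as "Assuming a 48% good quality blastocyst development rate and a 7% improvement in good quality blastocyst development with ZyMoT" and a phi correlation of 0.5. The result is 408 oocytes, equated to 68 dyads with 6 oocytes each.
- **Cohort size (5.3.1).** In the site's 2020 data, "The average number of mature oocytes within ICSI cycles with 6 or more mature oocytes obtained was 12 mature oocytes".
- **Preparation and culture (6.1.2).** Each dyad's semen is split once, into one ZyMot and one gradient preparation. Half the mature oocytes go to each. After injection, "one well will contain all oocytes inseminated with sperm selected by ZyMot device", and the gradient oocytes share another. After the fertilization check at 16-18 h, normally fertilized oocytes move to individual droplets.
- **Odd cohorts (6.1.2 and 6.1.3).** The extra oocyte goes to one arm according to the parity of the patient's identification number.
- **Additional model (6.4.3.2).** Under secondary analyses, the blastocyst rate is also to be analysed by a conditional logistic model fitted with GEE. Its stated purpose is "to account for both correlation between observations from the same patient and the size of the cohort of eggs from each patient". No rule says which result governs.
- **Interim (6.4.3.5 and 7.12).** Halfway through, the trial stops if good quality embryo formation is significantly lower with ZyMot. Section 7.12 gives p < 0.05; neither section names a test.

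**The concern.** McNemar's test takes its variance from the number of discordant pairs, so each oocyte pair counts as an independent trial of the device. The device, however, is used once per dyad and cycle. Pairing oocytes within a dyad cancels whatever raises or lowers both arms together, such as oocyte quality or the male partner's semen. It does not cancel what is common to the oocytes of one arm only, such as a good or poor run of that preparation. If such a component exists, the pairs of one dyad are correlated and the standard error leaves that correlation out.

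The test is also not fully specified. Without a pairing rule, the same data can give different discordant counts and so different p-values, and an unmatched oocyte has no place in the test.

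At stake are the p-value and interval behind the trial's main claim, and possibly the interim comparison that can end the trial.

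**Working it through.** **1. The plan's own figure.** Inputs from 6.4.2: p1 = 0.48, p2 = 0.55, so p = 0.515, q = 0.485 and d = 0.07; r = 0.5.

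n = 16pq(1 - r)/d² = 16 × 0.515 × 0.485 × 0.5 / 0.0049 = 407.8, rounded up to 408. The figure reproduces. At 6 oocytes per dyad this is 408/6 = 68 dyads with m = 3 pairs each. At the average of 12 (5.3.1) it is 408/12 = 34 cycles with m = 6 pairs each.

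**2. Variance under within-dyad pairing.** Let D be the ZyMot-minus-gradient difference of one pair. Let r be the correlation between oocytes of one dyad in different arms, s the correlation between oocytes of one dyad in the same arm, and v the outcome variance. Then Var(D) = 2v(1 - r), and two pairs of one dyad have covariance 2v(s - r). Their correlation is

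rho = (s - r)/(1 - r),

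and the true variance of the summed differences is McNemar's variance multiplied by

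VIF = 1 + (m - 1) × rho.

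A dyad effect common to both arms raises s and r equally and leaves rho at 0. Only a component specific to one arm within a dyad makes rho positive.

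**3. True error of a nominal 5% test:** 2 × [1 - Φ(1.96/√VIF)]. The documents give no rho, so the values below are assumptions. At r = 0.5 they correspond to s - r of 0.01, 0.025 and 0.05.

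| rho | VIF, m = 3 | Error, m = 3 | VIF, m = 6 | Error, m = 6 |
|---|---|---|---|---|
| 0 | 1.00 | 5.0% | 1.00 | 5.0% |
| 0.02 | 1.04 | 5.5% | 1.10 | 6.2% |
| 0.05 | 1.10 | 6.2% | 1.25 | 8.0% |
| 0.10 | 1.20 | 7.4% | 1.50 | 11.0% |

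**4. Simulation under no device effect.**

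- 34 dyads × 12 oocytes, 48% rate, patient SD 0.8 on the logit scale, 4,000 trials per setting. With a between-preparation SD of 0, 6.5, 10.7 and 14.4 percentage points (rho 0, 0.019, 0.051, 0.093), within-dyad McNemar rejected in 4.8%, 5.7%, 7.6% and 11.3% of trials. A patient-clustered test rejected in 4.5-5.6%.
- A separate set with a 50% rate and 20,000 trials per setting. With no preparation effect, within-dyad McNemar rejected in 4.8-5.2%, whatever the dyad SD. With a preparation SD of 0.5 logit it rejected in 5.8-6.3% (68 dyads × 3 pairs) and 7.2-8.5% (34 × 6). A dyad-level paired t-test stayed at 4.7-5.2% throughout.

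**5. Dependence on the pairing rule (second simulation set).** One pair per dyad rejected in 4.2-5.4% throughout. Random pairing across dyads rejected in 0.5-4.8% when the dyad effect was set to give a phi of about 0.5 before any preparation effect was added. With a smaller dyad effect (SD 1 logit) and a preparation SD of 1 logit, it rejected in up to 12.1%.

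**The case against.** The strongest reply is that the inflation is conditional and its driver is unmeasured. The sister-oocyte design removes patient effects, and if rho = 0 within-dyad McNemar is valid. ICSI also selects one sperm per oocyte, which may keep preparation effects small. The larger error rates need large effects: SDs of 10.7 and 14.4 points are about 1.5 and 2 times the whole 7-point target. At an SD of 6.5 points the simulated error is only 5.7%. At the 6 oocytes per dyad used for sizing, the assumed range gives 5.5-7.4%. Finally, 6.4.3.2 already plans a within-patient model for the same outcome.

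All of this stands as a limit on size. It does not remove the point: the test needs rho to be exactly zero, nothing in the documents supports that, and the planned model does not govern.

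Some stronger readings are tempting but not supported:

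- *That the p-value is too small under any pairing rule.* One pair per dyad is valid, though it discards most oocytes. Pairing across dyads can make the p-value too large.
- *That the trial has 34 independent comparisons rather than 204.* This needs rho = 1 (VIF 6, and 204/6 = 34). At rho of 0.02, 0.05 and 0.10, the 204 pairs are worth 204/1.10 = 185, 204/1.25 = 163 and 204/1.50 = 136.
- *That the shared well acts through to the endpoint.* Sharing ends at the 16-18 h check, well before grading on days 5 and 6.
- *That the interim uses an unadjusted McNemar test.* No test is named. The stop is for a worse result with ZyMot only, so it cannot itself produce a false efficacy claim.

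**Conclusion.** The point holds in conditional form. The primary test is an oocyte-level McNemar test with undefined pairing and no allowance for clustering. If pairs are formed within dyads, its p-value is too small whenever outcomes vary between preparations beyond what the two arms share, and correct if they do not. On the assumed range of rho, the true error is about 6% to 11% at 12 oocytes per dyad and 5.5% to 7.4% at 6. These figures assume within-dyad pairing, equal cohort sizes and a large-sample normal test. A reader should not infer that the error certainly exceeds 5%: the documents give no estimate of preparation-level variance. The missing pairing rule is a defect whatever the value of rho.

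**What to change.** In 6.4.3.1, make the primary test the between-arm difference in the good quality embryo proportion, with its standard error taken from patient-level differences and a t reference with (patients - 1) degrees of freedom. The patient is the cluster, with all of a patient's cycles together: 5.3.1 reports 137 retrievals from 121 patients in 2020, and no section limits a patient to one cycle. State whether patients are weighted equally or by number of oocytes. This test needs no pairing rule, uses odd cohorts in full and remains valid if rho = 0.

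Keep McNemar as supportive, with a stated pairing rule that says what happens to an unmatched oocyte. Name the same patient-clustered test for the interim comparison in 6.4.3.5 and 7.12.

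**Cost.** SAP wording, no new data and no further enrolment. The interval may be wider and the p-value larger. Even at rho = 0 and 34 patients, the t critical value is about 2.03 against 1.96, an interval about 4% wider (2.03/1.96 = 1.04). The statement in 6.4.2 that "the following relation yields an approximate power of 80% to detect a difference" was derived for McNemar and should be restated for the new test. At 12 oocytes per dyad and the assumed rho values, 408 oocytes carry the information of about 408/1.10 = 371, 408/1.25 = 326 or 408/1.50 = 272 oocytes under McNemar's assumptions.
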